The following by-subject listing will be provided:

- sPGA: date of completion, visit, language code, BMS scale identifier, scale question identifier, sub-scale score (I/E/S), and sPGA score.

7.5.2.5 DLQI

The following analyses will be provided:

- The DLQI score will be presented using the descriptive statistics (n, mean, median, min, max, standard deviation, Q1, Q3) for each group at Day 1 (baseline), Day 29, Day 57, Day 85, and Day 115. Point estimates for each visit and two-sided 95% CIs for mean change from baseline within each treatment group will be provided.
- A mixed effect model analysis with repeated measures will be performed to evaluate the impact of treatments on DLQI score over time. The model will be fit with treatment, visit, and treatment-by-visit interaction as the fixed effects and measurements (changes from baseline) within each subject as the repeated measurements. The baseline value, use of previous biologic treatment, study region, and use of previous biologic treatment-by-study region interaction will be added into the model as covariates. Based on the mixed effect model, the estimate and 95% confidence interval will be calculated for the difference between each active treatment and the placebo at each specified visit.

The following by-subject listing will be provided:

- DLQI: date of completion, visit, language code, BMS scale identifier, question 1-10, score total, and change from baseline.

7.5.2.6 BSA

The following analyses will be provided:

- BSA will be presented using the descriptive statistics (n, mean, median, min, max, standard deviation, Q1, Q3) for each group at Day 1, Day 8, Day 15, Day 29, Day 57, Day 85 and Day 115 for each group. Point estimates for each visit and two-sided 95% CIs for mean change from baseline within each treatment group will be provided.
- A mixed effect model analysis with repeated measures will be performed to evaluate the impact of treatments on BSA over time. The model will be fitted with treatment, visit, and treatment-by-visit interaction as the fixed effects and measurements (changes from baseline) within each subject as the repeated measurements. The baseline value, use of previous biologic treatment, study region, and use of previous biologic treatment-by-study region interaction will be added into the model as covariates. Based on the mixed effect model, the estimate and 95% confidence interval will be calculated for the difference between each active treatment and the placebo at each specified visit.

The following by-subject listing will be provided:

- BSA: date of assessment, visit, BSA result (%), and change from baseline.

[REDACTED]

[REDACTED]

[REDACTED]

[REDACTED]

[REDACTED]

[REDACTED]

[REDACTED]

[REDACTED]

[REDACTED]

[REDACTED]

[REDACTED]

[REDACTED]

[REDACTED]

[REDACTED]

[REDACTED]

[REDACTED]

[REDACTED]

[REDACTED]

[REDACTED]

[REDACTED]

[REDACTED]

[REDACTED]

[REDACTED]

[REDACTED]

[REDACTED]

[REDACTED]

7.5.4 Subgroup Analyses

To investigate the impact of study region (Japan vs rest of world) and the use of previous biologic treatment on the primary efficacy endpoint, subgroup analyses will be performed. The Cochran–Mantel–Haenszel Chi-square test on the response rates in PASI-75 at Day 85 will be conducted and the odds ratio (odd in a treatment group/odd in placebo) in the response rates and its corresponding two-sided 95% CI will be provided.

7.5.5 Sensitivity Analyses

If more than 10% of total subjects in the efficacy analysis population discontinued due to any reasons other than lack of efficacy, AE or unknown reason, a sensitivity analysis may be performed for the primary efficacy endpoint.

7.5.6 Per-Protocol Analyses

If at least 10% of total subjects in efficacy analysis population demonstrate relevant protocol deviations, a per-protocol analysis may be performed. A Per-protocol (PP) analysis population will exclude all subjects with at least one relevant protocol deviation (defined in Appendix 1) from the efficacy analysis population. A per-protocol analysis will be carried out for the primary efficacy

endpoint based on the PP analysis population. The grouping scheme will be the same as in the primary efficacy analysis.

7.6 Safety

Unless otherwise specified, the safety data will be presented using the As-Treated Analysis Population by treatment group, BMS combined treatment group, and all treated subjects combined. All AEs will be coded using version 19.1 of the Medical Dictionary for Regulatory activities (MedDRA) to a standard system-organ class (SOC) and preferred term (PT).

AEs are classified as treatment emergent (TEAEs) if they begin after the administration of study drug and within 30 days after the last dose.

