6 ADVERSE EVENTS

An *Adverse Event (AE)* is defined as any new untoward medical occurrence or worsening of a pre-existing medical condition in a clinical investigation subject administered study drug and that does not necessarily have a causal relationship with this treatment. An AE can therefore be any unfavorable and unintended sign (such as an abnormal laboratory finding), symptom, or disease temporally associated with the use of study drug, whether or not considered related to the study drug.

The causal relationship to study drug is determined by a physician and should be used to assess all adverse events (AE). The causal relationship can be one of the following:

Related: There is a reasonable causal relationship between study drug administration and the AE.

Not related: There is not a reasonable causal relationship between study drug administration and the AE.

The term "reasonable causal relationship" means there is evidence to suggest a causal relationship.

Adverse events can be spontaneously reported or elicited during open-ended questioning, examination, or evaluation of a subject. (In order to prevent reporting bias, subjects should not be questioned regarding the specific occurrence of one or more AEs.)

Sponsor or designate will be reporting adverse events to regulatory authorities and ethics committees according to local applicable laws including European Directive 2001/20/EC and FDA Code of Federal Regulations 21 CFR Parts 312 and 320.

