6.1.1 Serious Adverse Event Collection and Reporting

Sections 5.6.1 and 5.6.2 in the Investigator Brochure (IB) represent the Reference Safety Information to determine expectedness of serious adverse events for expedited reporting. Following the subject's written consent to participate in the study, all SAEs, whether related or not related to study drug, must be collected, including those thought to be associated with protocol-specified procedures. All SAEs must be collected that occur during the screening period and within 30 days of discontinuation of dosing.

The investigator must report any SAE that occurs after these time periods and that is believed to be related to study drug or protocol-specified procedure.

An SAE report must be completed for any event where doubt exists regarding its seriousness.

If the investigator believes that an SAE is not related to study drug, but is potentially related to the conditions of the study (such as withdrawal of previous therapy or a complication of a study procedure), the relationship must be specified in the narrative section of the SAE Report Form.

SAEs, whether related or not related to study drug, and pregnancies must be reported to Sponsor or designate within 24 hours of awareness of the event. SAEs must be recorded on the SAE Report Form; pregnancies on a Pregnancy Surveillance Form (electronic or paper forms). The preferred method for SAE data reporting collection is through the eCRF. The paper SAE/pregnancy surveillance forms are only intended as a back-up option when the eCRF system is not functioning. In this case, the paper forms are to be transmitted via email or confirmed facsimile (fax) transmission to:

SAE Email Address: Refer to Contact Information list.

SAE Facsimile Number: Refer to Contact Information list.

For studies capturing SAEs through electronic data capture (EDC), electronic submission is the required method for reporting. In the event the electronic system is unavailable for transmission, paper forms must be used and submitted immediately. When paper forms are used, the original paper forms are to remain on site

SAE Telephone Contact (required for SAE and pregnancy reporting): Refer to Contact Information list.

If only limited information is initially available, follow-up reports are required. (Note: Follow-up SAE reports must include the same investigator term(s) initially reported.)

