If an ongoing SAE changes in its intensity or relationship to study drug or if new information becomes available, the SAE report must be updated and submitted within 24 hours to Sponsor or designate using the same procedure used for transmitting the initial SAE report.

All SAEs must be followed to resolution or stabilization.

BMS will be reporting adverse events to regulatory authorities and ethics committees according to local applicable laws including European Directive 2001/20/EC and FDA Code of Federal Regulations 21 CFR Parts 312 and 320. A SUSAR (Suspected, Unexpected Serious Adverse Reaction) is a subset of SAEs and will be reported to the appropriate regulatory authorities and investigators following local and global guidelines and requirements.

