6.2.1 Nonserious Adverse Event Collection and Reporting

The collection of nonserious AE information should begin at initiation of study drug. Nonserious AE information should also be collected from the start of a placebo lead-in period or other observational period intended to establish a baseline status for the subjects.

Nonserious AEs should be followed to resolution or stabilization, or reported as SAEs if they become serious (see [Section 6.1.1](#)). Follow-up is also required for nonserious AEs that cause interruption or discontinuation of study drug and for those present at the end of study treatment as appropriate. All identified nonserious AEs must be recorded and described on the nonserious AE page of the CRF (paper or electronic).

Completion of supplemental CRFs may be requested for AEs and/or laboratory abnormalities that are reported/identified during the course of the study.

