6.7 Other Safety Considerations

Any significant worsening noted during interim or final physical examinations, electrocardiogram, x-ray filming, or any other potential safety assessment required or not required by protocol should also be recorded as a nonserious or serious AE, as appropriate, and reported accordingly.

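### SAP 7.6 tests onset only, so an SAE that starts in screening and worsens on study drug can miss the TEAE tables (minor)

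*SAP*

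**What the plan says.** **Treatment-emergent rule.** SAP 7.6: "AEs are classified as treatment emergent (TEAEs) if they begin after the administration of study drug and within 30 days after the last dose". The rule has no clause for an event already present at first dose that then gets worse or becomes serious.

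**What counts as an AE.** Protocol section 6: "any new untoward medical occurrence or worsening of a pre-existing medical condition in a clinical investigation subject administered study drug". Protocol 6.7 adds that significant worsening found on examination, ECG or another safety assessment "should also be recorded as a nonserious or serious AE, as appropriate, and reported accordingly".

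**When collection starts.** For non-serious events, Protocol 6.2.1: "The collection of nonserious AE information should begin at initiation of study drug". For serious events, Protocol 6.1.1 starts at consent: "All SAEs must be collected that occur during the screening period and within 30 days of discontinuation of dosing".

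**How a changing SAE is handled.** Protocol 6.1.1: "If an ongoing SAE changes in its intensity or relationship to study drug or if new information becomes available, the SAE report must be updated". The same section notes: "Follow-up SAE reports must include the same investigator term(s) initially reported".

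**Where the rule is applied.** The serious-event tables (SAP 7.6.2) and the overall and drug-related tables (SAP 7.6.5) are restricted to TEAEs. The tables of AEs leading to discontinuation (SAP 7.6.3) and to dose reduction or interruption (SAP 7.6.4) are not, and neither are the by-subject AE and SAE listings. Protocol 8.4.3 plans to list and tabulate every recorded AE, which is wider than the SAP's main tables.

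**The concern.** Safety and tolerability is one of the two primary objectives, and the TEAE tables are where AE incidence is compared by arm. An onset-only rule classifies an event correctly only if its recorded onset is the date on which the event, including a worsening, actually happened.

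SAE records can open before the first dose, and the protocol's instruction for a change in intensity is to update the open report. Nothing in that instruction moves the onset date or starts a new record. A deterioration on study drug could then sit in the database under a screening date and be left out of the by-arm counts. The listings would still show it, but listings do not give incidence by arm.

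**Working it through.** The main question is one of text, so I followed each kind of worsening through the rules.

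| Case | Recorded onset | Serious / overall TEAE tables | Elsewhere |
|---|---|---|---|
| Pre-existing condition worsens on drug; AE dated to the worsening | After dosing | Counted | Listings |
| Same, but site enters the underlying condition's onset date | Before dosing | Not counted | Listings |
| SAE starts in screening, is ongoing at first dose, worsens on drug; report updated | Before dosing, if the update leaves the onset unchanged | Not counted | Listings |
| Either uncounted case, leading to discontinuation, dose reduction or interruption | Before dosing | Not counted | Listings, plus the SAP 7.6.3 or 7.6.4 table |

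1. The first row is the ordinary one. Protocol section 6 makes the worsening itself the AE, and that AE begins when the worsening occurs. It passes the SAP 7.6 rule.
2. The second row depends on how the site dates the event. Non-serious collection starts with study drug, so a pre-dose onset should be unusual. Neither document says that the onset of a worsening is the date of worsening. SAP 8.4 sends missing and partial AE onset dates to an outside specification, but that reference concerns incomplete dates.
3. The third row follows from three provisions together: SAE collection from consent, updating of an ongoing report, and the onset-only rule. That the onset date survives the update is an inference, because the text is silent on it.

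**Size of one missed case.** With 42 subjects per arm (SAP section 5), one subject is 1/42 = 2.4 percentage points of an arm's incidence for that term, provided the subject has no other counted event under the same term. The documents give no basis for estimating how many such cases would arise.

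**The plan's own safety figures.** SAP section 5 gives the chance of at least one occurrence among 42 subjects, which is 1 − (1 − p)^42:

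- p = 1%: 1 − 0.99^42 = 34.4% (stated 34%)
- p = 5%: 1 − 0.95^42 = 88.4% (stated 88%)
- p = 10%: 1 − 0.90^42 = 98.8% (stated 99%)

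All three reproduce. They are probabilities of observing an event, and an event that appears only in a listing has still been observed.

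**The case against.** The strongest case against acting has four parts.

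- **The serious route is nearly empty.** It needs an SAE that starts in screening, is still ongoing at first dose, and leaves the subject eligible. Protocol 3.3.2 excludes significant acute or chronic illness, unstable conditions, recent major surgery, recent cardiac hospitalisation and recent serious infection. Protocol 3.3 allows no exceptions, and Protocol 5.3 requires a Day 1 review before randomization. This stands: the route should be rare, though it is not closed.
- **The non-serious route needs a poor date entry.** This also stands. The entry is one that the documents supplied do not rule out.
- **A convention may exist elsewhere.** Protocol 9.2.3 mentions study-specific CRF completion guidelines, which are not among the documents. They may already settle the onset date, so the finding is limited to what the protocol and SAP state.
- **The SAE provisions are reporting rules.** The note on keeping the same term follows a sentence about limited initial information and is separate from the rule on intensity. Neither states which onset date is kept. This is fair, and it is why the conclusion is that such an SAE can be missed, not that it will be.

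A reader might also infer that the stated 88% detection probability falls. If 10% or 20% of events of a 5%-incidence type were untabulated, the chance of at least one tabulated event would be 1 − 0.955^42 = 85.5% or 1 − 0.96^42 = 82.0%. The documents do not support using those numbers against the plan: both shares are pure assumptions, and the stated figure concerns observing an event, not tabulating it.

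**Conclusion.** The point holds as a minor gap. SAP 7.6 has no provision for an event that is present before first dose and worsens or becomes serious afterwards, and no onset convention for a worsening is stated in either document. A screening-onset SAE that worsens on drug can therefore be left out of the serious and overall TEAE tables, as can any worsening filed under the underlying condition's onset date.

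Two broader readings are tempting and do not hold. One is that the protocol and SAP definitions conflict, so that worsening in general drops out. They do not conflict, because a worsening is an AE that begins when it occurs. The other is that an uncounted event would be visible only in a listing. An event that led to discontinuation or dose modification is still tabulated, and safety is also judged from laboratory, ECG, vital-sign and examination data.

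The conclusion assumes that an updated SAE report keeps its onset date and that the unseen CRF guidelines do not already deal with the matter. The number of affected subjects cannot be estimated from the documents and should be small. No sample size, power or alpha changes.

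**What to change.** In SAP 7.6, define a TEAE as an AE that begins after first dose and within 30 days after the last dose, or one that was present before first dose and worsens in intensity or becomes serious within that period. State that the onset of a worsening is the date of worsening.

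Confirm that the CRF completion guidelines agree. If an update simply overwrites the existing record, the date of worsening may not be in the data and the SAP clause could not be programmed.

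The cost is one phrase in the SAP and a check of the guidelines, best done before unblinding. The downside is that a few more events may be counted as treatment emergent.

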7.6.1 Deaths

A by-subject listing of deaths will be provided for the All Enrolled Subjects population.

7.6.2 Serious Adverse Events

The following summary tables (counts and percentages) will be provided:

- Serious TEAEs summary by SOC/PT
- Serious drug-related TEAEs by SOC/PT

A by-subject SAE listing will be provided.

7.6.3 Adverse Events Leading to Discontinuation of Study Therapy

The following summary tables (counts and percentages) will be provided:

- AEs leading to discontinuation by SOC/PT

A by-subject listing of AEs leading to discontinuation of study therapy will be provided.

7.6.4 Adverse Events Leading to Dose Modification

The following summary tables (counts and percentages) will be provided:

- Summary of AEs leading to reduction and/or interruption by SOC/PT

A by-subject listing of AEs leading to dose reduction and/or interruption will be provided.

7.6.5 Adverse Events

The following summary tables (counts and percentages) will be provided:

- TEAEs summary of by SOC/PT
- Study drug-related TEAEs by SOC/PT

A by-subject AE listing will be provided.

7.6.6 Clinical Laboratory Evaluations

The following summary tables will be provided:

- Laboratory Test Results Summary of Marked Laboratory Abnormalities: hematology, liver and kidney function, and chemistry panel.

The following by-subject listings will be provided:

- Marked Laboratory Abnormality Criteria.
- Laboratory Listing by Lab Test.

- Subjects meeting marked laboratory abnormality criteria.
- Subjects with aspartate transaminase (AST)/alanine transaminase (ALT) > 3x upper limit of normal (ULN) and total bilirubin > 2xULN on the same date.

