6.6 Potential Drug Induced Liver Injury

Wherever possible, timely confirmation of initial liver-related laboratory abnormalities should occur prior to the reporting of a potential DILI event (see [Appendix 6](#) flow chart for sustained elevated liver safety abnormalities). All occurrences of potential DILIs, meeting the defined criteria, must be reported as SAEs (see [Section 6.1.1](#) for reporting details).

Potential drug induced liver injury is defined as:

1. Aminotransaminases (AT) (ALT or AST) elevation > 3 times upper limit of normal (ULN)
AND
2. Total bilirubin > 2 times ULN, without initial findings of cholestasis (elevated serum alkaline phosphatase),
AND
3. No other immediately apparent possible causes of AT elevation and hyperbilirubinemia, including, but not limited to, viral hepatitis, pre-existing chronic or acute liver disease, or the administration of other drug(s) known to be hepatotoxic.

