APPENDIX 6 SUSTAINED ELEVATED LIVER SAFETY ABNORMALITIES FLOW CHART

^a In subjects with repeat ALT or AST > 3X ULN but ≤ 10X ULN, only subjects with TB ≤ 2.0X ULN at Step 1 should be followed according to Step 2b. Subjects with an initial TB and confirmatory repeat TB > 2.0X ULN should be followed according to Step 2d.

^b additional assessments to be performed (AE assessment, PE, review of current medical history including focused review of risk factors for liver diseases and collection of blood samples [specialized liver panel or liver discontinuation panel](see below)).

^c Confirmatory repeat AST, ALT, ALK-P and TB should be obtained every 3 days following receipt of prior laboratory results, until the ALT and AST are ≤ 2X ULN or until ALT and AST are at or below baseline levels. The frequency of retesting can decrease to once a week or less if abnormalities stabilize and the subject is asymptomatic.

Specialized Liver Panel:

For subjects who are being monitored frequently as a result of confirmed AST and/or ALT > 3X ULN, additional central laboratory tests will be performed within 3 days of receipt of confirmatory results. These laboratory tests will study the possible causes of the increased ALT and/or AST and/or TB, and may include, but are not limited to, the following tests:

- Hepatitis A IgM
- Hepatitis BsAg
- Hepatitis B Core Ab IgM
- Hepatitis C virus RNA or RIBA
- Hepatitis C Ab
- Hepatitis E IgM
- Epstein-Barr Virus (EBV) IgM Ab
- Lactate Dehydrogenase (LDH)
- Gamma-glutamyl-transpeptidase (GGT)
- Carbohydrate deficient transferrin (CDT)
- Prothrombin time (PT/INR)
- Iron Panel - iron, ferritin, total iron binding capacity (TIBC)
- Immunology Panel including Antinuclear Antibody (ANA), Anti-Smooth Muscle Antibody (SMA) and Anti-Liver/Kidney Microsomal Antibody (Anti-LKM)
- Anti-tissue Transglutaminase Antibody

Liver Discontinuation Panel:

For subjects who are discontinued from the study as a result of sustained elevated liver safety abnormalities, additional central laboratory tests will be performed at the time of Early Termination (End-of-Treatment) visit. Similar to the Specialized Liver Panel, these laboratory tests will study the possible causes of the increased ALT and/or AST and/or TB, and may include, but are not limited to, the following tests:

- Cytomegalovirus (CMV) IgM Ab
- Herpes Simplex Virus (HSV) 1 and 2
- Ceruloplasmin
- Toxoplasmosis
- Alpha-1 antitrypsin

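### The SAP's paired AST/ALT and bilirubin listing needs both limits crossed on one date, a condition absent from the protocol's potential-DILI definition, so it may omit a subject whose bilirubin passes 2x ULN only after ALT and AST are back at 3x ULN or below

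*SAP*

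**What the plan says.** SAP 7.6.6 (Clinical Laboratory Evaluations) includes a by-subject listing of subjects with AST/ALT "> 3x upper limit of normal (ULN) and total bilirubin > 2xULN on the same date". It is the only output in the readable SAP that combines transaminases and bilirubin. The section plans no count by treatment group for the combination and does not say whether unscheduled draws enter it. It also plans a listing of all results by laboratory test and a summary and listing of marked abnormalities.

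Protocol 6.6 defines potential DILI by three conditions that must all hold:

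- "Aminotransaminases (AT) (ALT or AST) elevation > 3 times upper limit of normal (ULN");
- "Total bilirubin > 2 times ULN, without initial findings of cholestasis (elevated serum alkaline phosphatase");
- "No other immediately apparent possible causes of AT elevation and hyperbilirubinemia".

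None of the three carries a time condition. The section adds that "All occurrences of potential DILIs, meeting the defined criteria, must be reported as SAEs", and SAP 7.6.2 states that "A by-subject SAE listing will be provided".

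Protocol Appendix 6, footnote c, sets the repeat testing: "Confirmatory repeat AST, ALT, ALK-P and TB should be obtained every 3 days following receipt of prior laboratory results", continuing "until the ALT and AST are ≤ 2X ULN or until ALT and AST are at or below baseline levels". Retesting may drop to weekly or less often if values stabilise and the subject has no symptoms.

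**The concern.** Safety and tolerability form a primary objective in both documents (Protocol 1.3.1, SAP 3.1). A joint rise in transaminases and bilirubin is a liver signal for which a single case matters. The protocol follows a liver abnormality as a course over several draws. The listing looks at one date at a time, so a subject can cross both protocol thresholds during one episode and still not be listed.

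The SAE route depends on someone connecting results from separate draws and judging that no other cause is apparent. A listing driven by laboratory values is useful because it does not depend on that judgement. The same-date condition weakens it for sequential patterns.

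**Working it through.** No stated figure is at issue, so the check compares the rules.

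**Step 1: the two rules side by side**

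| Element | Protocol 6.6 | SAP 7.6.6 listing |
|---|---|---|
| Transaminases | ALT or AST > 3x ULN | AST/ALT > 3x ULN |
| Total bilirubin | > 2x ULN | > 2x ULN |
| Timing | none stated | same date |
| Initial cholestasis | must be absent | not considered |
| Other apparent cause | must be absent | not considered |

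The listing is narrower on timing and broader on cholestasis and cause.

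**Step 2: who falls between them**

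Let A(d) be the higher of ALT and AST, and T(d) total bilirubin, on date d, both in multiples of ULN.

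- SAP rule: some date d has A(d) > 3 and T(d) > 2.
- Protocol laboratory thresholds with no timing limit: some date d1 has A(d1) > 3 and some date d2 has T(d2) > 2.

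Everyone who meets the first rule meets the second. The difference is subjects who cross both limits but whose ALT and AST, on every date with bilirubin above 2x ULN, are both at or below 3x ULN or were not drawn. The order of the crossings does not matter.

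**Step 3: can the protocol's sampling produce this?**

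Yes. Appendix 6 keeps testing until ALT and AST are at or below 2x ULN, or at or below baseline. Draws therefore normally continue while transaminases lie between 2x and 3x ULN. A bilirubin above 2x ULN on such a draw, after an ALT or AST above 3x ULN, crosses both thresholds and fails the SAP rule.

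Split draws are less likely. AST, ALT and total bilirubin belong to one serum chemistry panel (Protocol 5.3.2), and Appendix 6 repeats them together.

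**Step 4: five illustrative courses**

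These are assumed values, not trial data. Cholestasis and other causes are taken as absent.

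| Course | Day: ALT / bilirubin (x ULN) | SAP rule | No timing limit |
|---|---|---|---|
| A, concurrent | 29: 5 / 2.4 | listed | listed |
| B, bilirubin later, ALT still > 3x | 29: 8 / 1.2; 32: 6 / 1.8; 35: 4 / 2.5 | listed | listed |
| C, bilirubin later, ALT between 2x and 3x | 29: 5 / 1.2; 32: 3.6 / 1.7; 35: 2.6 / 2.4 | not listed | listed |
| D, bilirubin later, ALT below 2x | 29: 4 / 1.2; 36: 1.8 / 2.3 | not listed | listed |
| E, split draws | 29: 5 / not drawn; 30: not drawn / 2.4 | not listed | listed |

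The SAP rule lists 2 of 5 and the rule without timing lists 5 of 5. The courses were chosen to show where the rules part, so 2 of 5 is not an estimate of sensitivity. Course B shows that delay alone does not cause an omission. Courses C and D show what does: transaminases at or below 3x ULN when bilirubin crosses.

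**The case against.** The case for leaving the listing alone has several parts.

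- **A delayed bilirubin rise is usually still caught.** A reader might infer that any subject whose bilirubin rises days after the transaminases is left out. The documents do not support that: if ALT or AST is still above 3x ULN on the draw where bilirubin passes 2x ULN, the subject is listed. This stands and limits the point to falling transaminases and, rarely, split draws.
- **The case does not vanish.** A reader might also infer that an omitted subject appears nowhere in the SAP output. That is wrong. The values are in the listing by test and may be in the marked-abnormality outputs, whose criteria are not visible. A case judged potential DILI must be reported as an SAE and is listed under SAP 7.6.2. An IDMC also reviews safety under its own charter and analysis plan, which are not available. This stands. None of the readable outputs, however, pairs the two tests across dates.
- **There is no formal contradiction.** SAP 7.6.6 neither calls this a DILI listing nor cites Protocol 6.6, and silence on timing is not a rule that any two dates count. This stands. The SAP nevertheless adopts the same two thresholds and gives no reason for the added condition.
- **An unconfirmed elevation may not qualify.** Protocol 6.6 asks for confirmation before reporting where possible, and Appendix 6, footnote a, turns on a repeat ALT or AST above 3x ULN. If the repeat is already below 3x ULN, whether the case is potential DILI is arguable, and the flow chart itself is not shown. This weakens course D. It does not remove course C, where the Day 32 repeat is 3.6x ULN.

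**Conclusion.** The point holds in a limited form. SAP 7.6.6 adds a same-date condition that Protocol 6.6 does not contain, so the listing may omit a subject who crosses both protocol laboratory thresholds on different draws. It narrows a check that does not rely on investigator judgement, for a primary safety objective.

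The frequency cannot be estimated from the documents. With the planned 42 subjects per arm and five active arms (5 x 42 = 210), one subject is 1/42 = 2.4% of an arm or 1/210 = 0.5% of active subjects. Those figures show only what one case weighs, not how likely one is.

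The conclusion assumes that the protocol's silence on timing means that no time limit applies, and that no redacted or separate output already pairs the tests across dates. No efficacy estimate, test, sample size or SAE reporting rule is touched. This is a cheap improvement of minor severity.

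**What to change.** In SAP 7.6.6, replace the same-date rule with a listing of all subjects who have any post-baseline AST or ALT above 3x ULN and any post-baseline total bilirubin above 2x ULN, in either order, including unscheduled and repeat draws. This matches Protocol 6.6, which states no window. For each subject show the dates of both crossings, the interval between them and alkaline phosphatase at those draws. Flag same-date cases so that the present listing can still be read off, and give counts by treatment group.

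If the sponsor prefers a time window, it should state and justify it as its own choice, since neither document supplies one.

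The cost is about one sentence in the SAP and a small programming change. The downside is that a few more subjects without DILI will be listed, for instance with unrelated crossings far apart in time, and will need medical review. The interval column makes these easy to recognise.
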